Table 3 outlines the key information on vaccination exposure, integrated into the COPS study database from the National Services Scotland (NSS) National Clinical Data Store (NCDS).

Table 3: Exposure variables

Variable	Definition	Notes
Dose 1 received	No Yes	Exposure variable for inclusion in model Additional exposure variables for inclusion in database, descriptive analyses and any further investigation, where appropriate.
Vaccination date dose 1	dd/mm/yyyy	
Vaccine batch number 1	Unique alphanumerical code assigned to each vaccine batch	
Vaccine type 1	Pfizer/ BNT162b2 AstraZeneca/ ChAdox1nCov-19 Moderna Janssen	
Vaccination class 1	mRNA (Pfizer and Moderna) Viral Vector (AstraZeneca and Janssen)	
Dose 2 received	No Yes	
Vaccination date dose 2	dd/mm/yyyy	
Vaccine batch number 2	Unique alphanumerical code assigned to each vaccine batch	
Vaccine type 2	Pfizer/ BNT162b2 AstraZeneca/ ChAdox1nCov-19 Moderna Janssen	
Vaccination class 2	mRNA (Pfizer and Moderna) Viral Vector (AstraZeneca and Janssen)	
Dose 3 received*	No	

	Yes	
Vaccination date dose 3*	dd/mm/yyyy	
Vaccine batch number 3*	Unique alphanumeric code assigned to each vaccine batch	
Vaccine type 3*	Pfizer/ BNT162b2 AstraZeneca/ ChAdox1nCov-19 Moderna Janssen	
Vaccination class 3*	mRNA (Pfizer and Moderna) Viral Vector (AstraZeneca and Janssen)	

*Currently disaggregation by whether this was a third dose or a booster dose is not available in the COPS study database but as these data become available we will further stratify by third dose and booster dose.

3.5.3: Covariates

Covariates of importance are shown in Table 4. Note that covariate groupings will be collapsed into fewer groups where clinically appropriate to do so. Prior to statistical modelling, each covariate will be examined for collinearity.

Table 4: Covariates of interest

Covariate	Category	Notes
Deprivation Score	SIMD 1 - most deprived	
	SIMD 2	
	SIMD 3	
	SIMD 4	
	SIMD 5 - least deprived	
	Unknown	
Maternal urban-rural status	Large Urban Areas	Regrouping as binary variable to be explored.
	Other Urban Areas	
	Accessible Small Towns	
	Remote Small Towns	
	Very Remote Small Towns	
	Accessible Rural Areas	
	Remote Rural Areas	
	Very Remote Rural Areas	
	Unknown	
Maternal ethnicity	White Scottish	Regrouping into fewer categories to be explored.
	White Other British	
	White Other	
	South Asian	
	Chinese	
	Black/Caribbean/African	
	Mixed or other ethnic group	
	Unknown	

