Maternal pre-pregnancy clinical vulnerability (excluding diabetes)	Clinically extremely vulnerable (on shielding list)	
	Clinically vulnerable (Q-COVID comorbidity excluded diabetes or hypertension)	
	Not clinically vulnerable	
Diabetes	Yes – pre-existing diabetes	If we only have a small number of women that are identified as having diabetes but it is unknown as to whether this is gestational or pre-existing, then we will combine gestational diabetes & unknown diabetes groups.
	Yes – gestational diabetes	
	Yes – diabetes onset unknown	
	No diabetes	
BMI at antenatal booking	Underweight (<18.5) Healthy weight (18.5-<25) Overweight (25-<30) Obese (30-<40) or severely obese (≥40) Unknown	Obese and severely obese will be combined.
Smoking at antenatal booking	Yes - current	
	Yes - former	
	No - never	
	Don't know	

Note: categories will be collapsed as required.

We have considered, but are currently not planning to include, several other covariates. These include parity and pregnancy-related complications other than gestational diabetes. Information on parity is only available on delivery records, negating its inclusion for any of the early pregnancy outcomes, and there are concerns about the quality of these data. Theoretically, pregnancy-related complications (e.g. pregnancy-induced hypertension and pregnancy-related bleeding) could be on the causal pathway between vaccination status and other adverse outcomes so will not be included as potential confounders. However, additional analyses will be conducted as appropriate if we see signals of associations between vaccination and outcomes that might be due to differential vaccination uptake in women with pregnancy-related complications. Gestational diabetes was considered as an exception to this and included as a covariate. This is because pregnant women with gestational diabetes were added to the list of individuals clinically vulnerable and therefore eligible for vaccination in priority risk group 6 early in the vaccination programme (March 2021), possibly leading to high uptake in this group, and the known association between diabetes and many of the outcomes under study.

3.6: Cohort study matching

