*Note that only women who have been followed-up to the end of the outcome-specific follow-up period at the end of each study period (i.e. 29 February 2020 for pre-pandemic controls and data of data extraction for pandemic controls) are eligible to be controls for a given outcome analysis.

3.7: Power calculation for matched cohort

It is estimated that by the end of 2021, full outcome and follow-up data will be available for approximately 5,000 vaccinated pregnant women, and by end of 2022, data available for 10,000 vaccinated pregnant women⁶.

Outcomes can be grouped as frequent (risk approximately 10%), moderate (approximately 3%), and rare (approximately 0.5%). Risk estimates for each adverse outcome are provided in Table 2. Based on these estimates and assumptions, with the relative risk of an event occurring post-vaccination set at 0.5, 1.2 and 2.0, and with statistical significance set at 0.05 and 0.01; power calculations for the various scenarios were calculated and are shown in Table 6. The power to detect a relative risk of 0.5, based on 5000 vaccinated pregnant woman against 15000 controls (ratio 1:3), when estimated

⁶ Personal communication with [name], July 2021.

adverse event occurrence is 0.5%, is 94%. This means that the study has a 94% chance of having a p-value of less than 5% (a statistically significant result and strong evidence against the null hypothesis) if there is really a difference in risk between vaccinated and unvaccinated women.

If the statistical power is low, the study sample size may be too small to detect any differences (i.e. under-powered) and therefore null results will need to be interpreted with caution. By convention, 80% is an acceptable level of power. It is acknowledged that the study may be under-powered to identify rarer outcomes.

Table 6: Power calculations scenarios

Cases	Controls	Estimated risk	Relative risk	Power %
5000	15000	0.50%	0.5	94
			1.2	10
			2.0	66
		3.00%	0.5	100
			1.2	45
			2.0	100
		10.00%	0.5	100
			1.2	94
			2.0	100
10000	30000	0.50%	0.5	100
			1.2	17
			2.0	94
		3.00%	0.5	100
			1.2	75
			2.0	100
		10.00%	0.5	100
			1.2	100
			2.0	100

4.0: Data Analyses

4.3: Descriptive analyses

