First, a model with no covariates will be fitted to calculate the unadjusted OR for the association between vaccination status and each outcomes of interest. Subsequently, we will calculate an adjusted OR for the association between vaccination status and each outcomes of interest, by adding all covariates to the model (Table 4). P-values and confidence intervals will be reported for all models. For some rarer outcomes, we will adjust our modelling approach as required (e.g. re-classification of groupings or removing insignificant covariates). Covariate pairs will be assessed for collinearity before adding to the model. For any covariate pairs that are highly correlated, only the covariate which has the biggest impact on the association between the exposure and outcome will be included in the model.

As previously described (section 3.5.2), analyses will be conducted first looking at the association between having any vaccination and outcomes, and then in sub-group analyses stratified by vaccine classes and individual vaccine types;

- Vaccine type: Pfizer, AstraZeneca, Moderna, Janssen
- Vaccine group: Pfizer and Moderna (mRNA); AstraZeneca and Janssen ((adeno)virus vector)
- Number of vaccine doses

Our main analyses will include all pregnancies/births, regardless of whether there is evidence that it was singleton or multiple, with sensitivity analyses conducted restricting to only pregnancies/births where there was no evidence it was a multiple. We often do not know whether pregnancies which end early (e.g. due to miscarriage) were singleton or multiple, hence the decision to only include pregnancies with *no evidence* of being a multiple in these sensitivity analyses.

4.5: Additional analyses

There are two further analyses that may subsequently be conducted to assess the association between vaccination and adverse outcomes, specifically:

1. We will consider using all data from the pre-pandemic period to predict the expected number of outcomes among the vaccinated pregnant women, and compare this predicted number to the observed number within the vaccinated group of women.
2. For rarer outcomes (e.g. for congenital anomalies, microcephaly), we will consider a nested case control study if signals are identified in this present matched cohort analysis but wide confidence intervals due to the small number of events negate any meaningful conclusions. This design maximises power to assess any association between vaccination and these rare outcomes.

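### For rarer outcomes, dropping covariates because they are non-significant can leave measured confounding in the adjusted odds ratio

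*Protocol*

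**What the plan says.** Section 4.4 of the Protocol fits an unadjusted model for each outcome and then an adjusted one, formed "by adding all covariates to the model (Table 4"). It then makes an exception: for some rarer outcomes the model may be changed where needed, and the examples given are "re-classification of groupings or removing insignificant covariates". It gives no p-value threshold and names no covariate that must stay.

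Three other statements bear on this:

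- Section 3.5.3 already permits coarser categories: "Note that covariate groupings will be collapsed into fewer groups where clinically appropriate to do so".
- The same section argues for keeping gestational diabetes from prior knowledge, citing its early priority for vaccination and "the known association between diabetes and many of the outcomes under study".
- Section 3.7 accepts that the study may lack power for rarer outcomes and that null results then call for caution.

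Section 4.4 also has a separate rule for highly correlated covariate pairs, discussed under the objection.

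**The concern.** A confounder matters through two things: how unequally it is spread between vaccinated and unvaccinated women, and how strongly it predicts the outcome. Its p-value in the outcome model measures neither directly. With few events the p-value is governed mainly by the number of events, so a test at the usual level will discard moderate confounders most of the time.

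The provision therefore applies where the test is least informative. It also conflicts with the protocol's own reasoning: diabetes is included because it is known to matter, yet for a rare outcome it could be dropped because 30 or 80 events fail to show that it matters.

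At stake is the adjusted odds ratio for the rarer safety outcomes. If covariates are removed this way, the estimate moves back toward the crude one, the adjustment set can differ between outcomes, and the 95% intervals take no account of the selection. If vaccinated women are at lower baseline risk, the residual confounding pulls the odds ratio below 1, which is the unhelpful direction for a safety study.

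**Working it through.** **The plan's own figures.** The protocol gives no figure for the covariate rule, so there is none to reproduce. Only the cohort sizes and risks are used here. (The 94% power quoted in section 3.7 for a relative risk of 0.5 concerns the vaccine effect and does not enter. It does not reproduce as labelled: vaccinated risk over control risk gives 66.5%, the inverse 94.8%. That is a separate matter.)

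**Step 1. Expected events under no vaccine effect.** Events = 20,000 × risk, with 5,000 vaccinated and 15,000 controls (section 3.7) and risks from Table 2 or, for the last row, section 3.7.

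| Outcome | Risk | Events |
|---|---|---|
| Venous thromboembolism | 0.15% | 30 |
| Neonatal death | 0.2% | 40 |
| Stillbirth; severe microcephaly | 0.4% | 80 |
| Rare category | 0.5% | 100 |

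**Step 2. Is some reduction needed?** Yes. Table 4 uncollapsed, with unknown as a level, has 5 + 8 + 7 + 2 + 3 + 4 + 3 = 32 indicator terms. With the vaccine term that is 33, giving 30/33 = 0.9 events per term for venous thromboembolism and 100/33 = 3.0 for the rare category. The question is how to reduce the model, not whether to.

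**Step 3. Chance that a real confounder is dropped.** Assumptions, not in the protocol: binary confounder, prevalence 10% in vaccinated women and 20% in controls, outcome OR 1.5, dropped if p ≥ 0.05.

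- Pooled prevalence = 0.25 × 0.10 + 0.75 × 0.20 = 0.175.
- Share of events carrying the confounder = 0.175 × 1.5 / (0.825 + 0.175 × 1.5) = 0.241.
- Variance of the log OR ≈ (4/3) × (1/a + 1/b), where a and b are events with and without the confounder and 4/3 approximates the cost of 1:3 matching.
- 30 events: a = 7.2, b = 22.8, SE = 0.493, z = 0.405/0.493 = 0.82. Kept: Φ(0.82 − 1.96) = 13%; dropped 87%.
- 100 events: a = 24.1, b = 75.9, SE = 0.270, z = 1.50. Kept: 32%; dropped 68%.

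Simulated 1:3 conditional logistic regression (1,500 runs per scenario) agrees: dropped 89% at 30 events, 69% at 100 and 48% at 200. For a confounder with OR 2.0 the simulated figures are 72%, 31% and 5%.

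**Step 4. Effect on the vaccine odds ratio.** True OR 1, same simulation, confounders less common in vaccinated women:

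| Scenario (confounder OR 1.5) | All kept | Selected | Crude |
|---|---|---|---|
| 100 events, one | 0.997 | 0.977 | 0.950 |
| 100 events, three | 0.991 | 0.933 | 0.860 |
| 100 events, three, stronger imbalance | 0.990 | 0.912 | 0.820 |
| 30 events, three | 0.962 | 0.879 | 0.829 |

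Share of confounding left in = (all kept − selected)/(all kept − crude). In the second row this is 0.058/0.131 = 44%; in the last, 0.083/0.133 = 62%. For one confounder of OR 2.0 at 100 events it is only about 15%.

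Other assumed settings, by unconditional logistic approximation, true OR 1:

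- Five confounders of OR 1.5, all more common in vaccinated women (45% v 30%), 33 events: median OR 1.18 selected v 1.01 with all kept; coverage 90% v 95%. At 88 events: 1.11 v 0.99; coverage 90% v 96%. Another set of runs of the all-one-direction case gave 1.14 and 1.09.
- Same strength, three pushing up and two down: 1.02 to 1.06 in one set of runs, 1.00 in another.
- Five-point imbalance, all one way: 1.02 to 1.05; coverage 95–96%.

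**Step 5. Does dropping buy precision?** SD of the log OR, selected v all kept: 0.427 v 0.426 (33 events), 0.262 v 0.252 (88 events), 0.264 v 0.261 (97 events, three confounders). No gain.

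**Step 6. Does the alternative work?** One propensity-score term matched the all-kept model within 0.005 on the OR in the settings where it was tried (1.005 v 1.009 at 33 events), with the same coverage. The score model can be fitted however rare the outcome: 5,000/32 ≈ 156 vaccinated women per term.

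**The case against.** The strongest reply is that this is an optional fallback. The default is full adjustment. Removal is one of two examples, used as required, for some rarer outcomes, and the other example, regrouping, is harmless. A reader might infer that the adjusted odds ratios for rare outcomes will be biased. The protocol does not support that: it shows only that they can retain confounding. This part of the objection stands.

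It also stands that the size cannot be fixed from the protocol. The 18% figure needs five confounders all pushing one way; mixed directions largely cancel. Even 18% is log 1.18 = 0.17 against an SD of 0.43, and in the conditional simulation at 100 events the type I error stayed between 0.045 and 0.067.

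A reader might also infer that the rule for correlated pairs, by which "only the covariate which has the biggest impact on the association between the exposure and outcome will be included in the model", causes the same bias. It does not. It is a change-in-estimate rule with no significance test, it applies to all outcomes, and the covariate kept carries most of the information of the one dropped. In simulation it chose the true confounder only 58–72% of the time at 30–100 events, but the added bias was under about 1%.

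The sparsity argument stands in part. An unpenalised model with all 32 terms is unworkable, and the precision comparison in step 5 used only three or five binary terms. The conditional multinomial model planned for stillbirth was not simulated. This rules out keeping every term as it is; it does not justify choosing terms by p-value.

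The other safeguards (the crude odds ratio, descriptive tables by covariate, caution about low power, possible nested case-control work) make imbalance visible but do not remove it from the adjusted estimate.

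**Conclusion.** The point holds, confined to significance-based removal. With about 30 to 100 events, a moderate real confounder (OR 1.5) would usually be dropped, and the adjusted odds ratio can keep confounding that Table 4 already measures. Under the assumed scenarios the shift ran from about 1% to 18% (upward to 18%, downward to about 9%), usually smaller than the standard error, with no gain in precision.

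This rests on assumed prevalences, strengths and directions and on a 5% removal threshold, none of which the protocol gives. The event counts rest on the protocol's own risks and on 5,000 vaccinated women; at 10,000 they double and the problem eases. It is worth correcting because the method named is a poor one and a better one costs little. It is not evidence that any reported result will be wrong.

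**What to change.** In section 4.4, delete the words on removing insignificant covariates, keep the regrouping example, and state that for rare outcomes model size will be reduced without reference to covariate p-values. Then name one of two routes:

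1. Collapse categories, as section 3.5.3 already allows, and adjust through a single propensity-score term for vaccination built from the Table 4 covariates.
2. Name in advance, on subject-matter grounds, a reduced covariate set that stays whatever its p-values, and fit it by Firth-type penalised conditional logistic regression.

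The cost is a change of wording and one extra propensity or penalised fit per rare outcome; no new data are needed. As an optional tidy-up, choose between highly correlated covariates on subject-matter grounds before the vaccine estimate is seen.

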5.0 Potential limitations

There are a number of limitations that need to be considered when conducting the analysis and interpreting the results. Some of the key limitations are as follows:

1. Lag in data becoming available for women recently captured within the COPS study database:
Due to the way the COPS cohort is derived, there is a lag of up to three months before conceptions are identified and hence the corresponding pregnancies included in the study dataset. This is because either antenatal booking, or an early spontaneous pregnancy loss or termination of pregnancy prior to booking, must occur, and the relevant record be returned to PHS, prior to the pregnancy being identified and the conception retrospectively imputed. These events will usually occur within three months of conception. The COPS cohort is refreshed monthly: more frequent refreshes are not feasible as key source datasets (in particular SMR02) are only updated monthly. This means that, using any month's COPS cohort plus up-to-date vaccination data, will likely fail to identify some recent vaccination events as occurring during early pregnancy. These will be picked up in subsequent months as the COPS cohort is refreshed. This means that initial data outputs must be understood as provisional.
2. Capture of early pregnancy loss:
Women who have early pregnancy loss and do not seek medical advice will not be captured in the COPS dataset.
3. Insufficient sample size for rare outcomes:
For rarer outcomes, there may be insufficient power to assess the association between vaccination status and the outcome using a matched cohort study design. We will still provide descriptive data for these outcomes and, as mentioned in Section 4.5, we will consider different analytical approaches for rare outcomes.
4. Missing data:
For some covariates, there will be missing data, but this is expected to be minimal based on ongoing assessments of data quality.
5. Recording errors:

There may be errors in recording the pregnancy, maternity or neonatal outcomes and the way in which outcomes are recorded may have changed over time.

6. Unmeasured confounding:

There is the potential for unmeasured confounding given the inherent differences between vaccinated and unvaccinated women which might not be accounted for. Specific examples include occupation, specific comorbidities, and wider healthcare seeking behaviours including engagement with antenatal care.

6.0 Publication of results

Core information on vaccine uptake and coverage among pregnant women is published in the PHS COVID-19 weekly report on a monthly basis.

All interim and final results will be shared with the PHS Vaccine Safety Advisory Group and potentially other key stakeholders including:

- The Clinical Governance Group for the Flu Vaccine COVID Vaccine (FVCV) programme. The group is responsible for providing clinical oversight for the delivery of the vaccination programme. This group meets weekly to discuss clinical issues of importance (e.g. any arising safety issues and any actions required) and involves senior PHS, National Services Scotland (NSS) and Scottish Government colleagues.
- Medicines and Healthcare products Regulatory Agency (MHRA). If a signal is detected in these analyses, it may be useful to share with MHRA colleagues to see if they have further intelligence on this.
- Four-nations working group on vaccine safety in pregnancy. The other UK nations are also planning similar analyses and so a discussion on results would be useful.
- EAVE steering group. EAVE-II is a collaborative study involving PHS and Scottish universities to answer important questions on COVID-19 using linked national data.
- DaCVaP steering group. DaCVaP is a collaborative study within the suite of COVID-19 national core studies that is conducting UK wide studies on vaccine safety and effectiveness.
- Global Vaccine Data Network. This is a network of sites that contribute to globally coordinated active surveillance epidemiologic studies of the safety of vaccines, including COVID-19 vaccines. Sharing of information for potential inclusion in meta-analyses to generate global estimates of the risk of AESI following COVID-19 vaccination.

Appendix 1: ICD 10 codes to identify admissions due to pregnancy-related bleeding, maternal venous thromboembolism, and hypertensive disorders of pregnancy

Appendix Table 1: ICD-10 codes for identifying pregnancy-related bleeding

ICD-10	Condition
	Obstetric haemorrhage
O44.1	Placenta praevia with haemorrhage
O45.0	Premature separation of placenta with coagulation defect
O45.8	Other premature separation of placenta
O45.9	Premature separation of placenta, unspecified
O46.0	Antepartum haemorrhage with coagulation defect
O46.8	Other antepartum haemorrhage
O46.9	Antepartum haemorrhage, unspecified
O67.0	Intrapartum haemorrhage with coagulation defect
O67.8	Other intrapartum haemorrhage
O67.9	Intrapartum haemorrhage, unspecified
O69.4	Labour and delivery complicated by haemorrhage from vasa praevia
O72.0	Third stage haemorrhage
O72.1	Other immediate postpartum haemorrhage
O72.2	Delayed and secondary postpartum haemorrhage
O72.3	Postpartum coagulation defects
O44.1	Placenta praevia with haemorrhage
	Early pregnancy bleeding
O03.1	Incomplete spontaneous abortion (miscarriage), complicated by haemorrhage
O03.6	Complete spontaneous abortion (miscarriage), complicated by haemorrhage
O04.1	Incomplete medical abortion (TOP), complicated by haemorrhage
O04.6	Complete medical abortion (TOP), complicated by haemorrhage
O05.1	Incomplete other abortion, complicated by haemorrhage
O05.6	Complete other abortion, complicated by haemorrhage
O06.1	Incomplete unspecified abortion, complicated by haemorrhage
O06.6	Complete unspecified abortion, complicated by haemorrhage
O07.1	Failed medical abortion, complicated by haemorrhage
O07.6	Other and unspecified failed medical abortion, complicated by haemorrhage
O08.1	Delayed or excessive haemorrhage following abortion and ectopic and molar pregnancy
O20.0	Threatened abortion
O20.8	Other haemorrhage in early pregnancy
O20.9	Haemorrhage in early pregnancy, unspecified
	Disseminated intravascular coagulation
D65	Disseminated intravascular coagulation
	Considered but not included
O43.2	Morbidly adherent placenta
O69.5	Labour and delivery complicated by vascular lesion of cord

